7.0 Safety Analysis

All the safety parameters presented below will be descriptively presented for each treatment level using Safety population in this study. No comparison will be done between levels, therefore no statistical tests will be reported for the safety parameters.

Page 19 of 22

7.1 Adverse Events

Adverse event reports will be coded using the most recent version of the Medical Dictionary for Regulatory Activities (MedDRA Version 22.1) and presented by system and organ class (SOC) and preferred term. The severity of all AEs will be characterized and classified into one of three defined categories as Mild. Moderate and

The severity of all AEs will be characterized and classified into one of three defined categories as Mild, Moderate and Severe.

The causality of all AEs to the study drug will be classified into one of three defined categories as Unlikely, Possible and Probable.

A Treatment-emergent AE (TEAE) is defined as an event which occurred following the first dosing of study treatment, or that started prior to the first dosing and worsened during the treatment.

An overall summary of AEs during the trial will be presented by treatment level. This summary will include the number and percentage of patients with any AEs, a TEAE, a serious TEAE, a related TEAE, a serious related TEAE, a TEAE leading to discontinuation and a TEAE leading to death.

The number and percentage of patients reporting TEAEs will also be presented by treatment level. Frequency tables of TEAEs will be presented by treatment level, MedDRA system organ class and preferred term and will include the number and percentage of patients report the event. The same summary tables will also be presented for serious TEAEs, related TEAEs, serious related TEAEs, TEAEs leading to discontinuation and TEAEs leading to death.

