^a Mean exposure for male and female rats combined on last day of study

^b Mean exposure for patients after 100 mg b.i.d. dose of PTI-125 on Day 28 (CSR PTI-125-03)

A 28-day repeat dose oral toxicity study in dogs that included a 28-day drug-free recovery period used PTI-125 dose levels up to and including 200 mg/kg/day (equivalent to 4,000 mg/m²). Findings included slight muscle fasciculations in some animals at the high dose only, an increase in blood pressure in high dose females, and sporadic alterations in clinical chemistry profiles at the high dose. All observations resolved during the recovery period. A NOEL could not be determined, and the NOAEL was determined to be 100 mg/kg/day (equivalent to 2,000 mg/m²). Safety margins based on this study are shown in **Table 2**.

Table 2. Safety Margin for a 100 mg b.i.d. Human Dose Based on the 4-week Dog Tox

| NOAEL (mg/kg) | C _{max} (ng/mL) | | AUClast (h) | r*ng/mL) | Dog-to-Human Ratio (Safety Margin) | | |
|------------------|--------------------------------|-------|------------------|--------------------|---------------------------------------|---------------------|--|
| | mg/kg) Dog ^a Hui | | Dog ^a | Human ^b | C _{max} | AUC ₀₋₂₄ | |
| 100 | 49,000 | 1,104 | 214,000 | 8,483 | 44.4 | 25.2 | |

^a Mean exposure for male and female dogs combined on last day of study

^b Mean exposure for patients after 100 mg b.i.d. dose of PTI-125 on Day 28 (CSR PTI-125-03)

A subsequent 13-week repeat dose oral toxicity study with a 28-day recovery in dogs used doses of 25, 75 and 150 mg/kg/day. The toxicological response was characterized primarily by increased incidence of emesis and salivation (sometimes extreme), and decreased food consumption in 150 mg/kg animals (reversible). There were occasional incidences of muscle fasciculations, and a few isolated incidences of tremors, lying down, reluctance to stand, and hypoactivity (generally slight). Based the severity and time course of these observations, the NOAEL was established at 150 mg/kg/day. The Day 90 C_{max} at this dose was 70.3 and 71.8 µg/mL in males and females, respectively, and the Day 90 AUC_{last} was 456 and 439 h•µg/mL in males and females, respectively. Safety

margins based on this study are shown in Table 3.

| NOAEL (mg/kg) | C _{max} (ng/mL) | | AUClast (h) | r*ng/mL) | Dog-to-Human Ratio (Safety Margin) | | |

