9.2. Adverse Events - Severity Rating

The severity of each AE should be characterized and then classified into one of three clearly defined categories as follows:

- Mild the AE does not interfere in a significant manner with the subject's normal functioning level. It may be an annoyance.
- Moderate the AE produces some impairment of functioning but is not hazardous to health. It is uncomfortable or an embarrassment.
- Severe the AE produces significant impairment of functioning or incapacitation and is a definite hazard to the subject's health.

These three categories are based on the Investigator's clinical judgment, which in turn depends on consideration of various factors such as the subject's report, and the physician's observations. The severity of the AE should be recorded in the appropriate section of the Adverse Event CRF.

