4.3.4 Missing Data

Missing data will not be imputed for the purpose of this analysis. All data recorded on the electronic case report form (eCRF) will be included in data listings that will accompany the clinical study report, as applicable. For qualitative parameters, a category with the number of patients with missing values will be presented where applicable.

Missing data imputations for Adverse Events will be included in the TEAE. Instead, the data will be presented in the AE listings.

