4.4 Planned Analyses

4.4.1 Statistical Summaries: Descriptive and Inferential

All statistical tests will be two-sided and a difference resulting in a p-value of less than or equal to 0.05 will be considered statistically significant.

All p-values will be rounded to and displayed in four decimals. If a p-value less than 0.0001 occurs, it will be shown in tables as <0.0001.

Descriptive summaries of variables will be provided where appropriate. For continuous variables, the number of nonmissing values (n) and the median, mean, standard deviation, minimum, and maximum will be tabulated by treatment. For categorical variables, the counts and proportions of each value will be tabulated by treatment.

Data will be presented as listings where applicable. Data not subject to analysis according to this plan will not appear in any tables or graphs but will be included in the data listings.

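### SAP 7.1 has every adverse event graded for severity but specifies no summary by severity and treatment arm, so the grade is assured only in the data listings

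*SAP*

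**What the plan says.** Protocol 9.2 defines three severity grades and requires the grade to be captured: "The severity of the AE should be recorded in the appropriate section of the Adverse Event CRF". The top grade is a strong statement; under it, "the AE produces significant impairment of functioning or incapacitation and is a definite hazard to the subject's health". SAP 7.1 carries the grading over: "The severity of all AEs will be characterized and classified into one of three defined categories as Mild, Moderate and Severe". It introduces causality in the same way, also in three categories.

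SAP 7.1 then lists what will be tabulated by treatment level. For the overall summary: "This summary will include the number and percentage of patients with any AEs, a TEAE, a serious TEAE, a related TEAE", followed by serious related TEAEs, TEAEs leading to discontinuation and TEAEs leading to death. For the frequency tables by system organ class (SOC) and preferred term (PT), after the table of all TEAEs: "The same summary tables will also be presented for serious TEAEs, related TEAEs, serious related TEAEs, TEAEs leading to discontinuation and TEAEs leading to death".

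Two general rules decide what happens to a recorded item that has no table. SAP 4.4.1: "Data not subject to analysis according to this plan will not appear in any tables or graphs but will be included in the data listings". SAP 4.3.4 says that recorded eCRF data, as applicable, "will be included in data listings that will accompany the clinical study report".

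SAP 7.0 says that the safety parameters in that section are described by treatment level, with no between-arm tests. SAP 8.0 leaves the list of displays to a separate mock-TLF document.

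**The concern.** Safety is the first-listed primary objective in SAP 1.1, and the trial compares two active doses with placebo. Because SAP 7.0 plans no safety tests, the descriptive tables are the whole by-arm account of adverse events.

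Severity and seriousness are different attributes. Protocol 9.4 defines seriousness by outcome (death, threat to life, admission, disability, congenital anomaly) or by medical judgement. An event can be graded severe, meet none of these and not lead to discontinuation. In the tables that SAP 7.1 names, it then counts as a TEAE, and as a related TEAE where that applies, exactly as a mild event of the same term does. If the arms differ in how bad such events are rather than in how many patients have them, those tables cannot show it. Someone would have to notice it in the listings and count.

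**Working it through.** There is no stated figure to reproduce, because the point is about which displays are specified. The check is an inventory, followed by a hypothetical example for scale.

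**1. Displays named in SAP 7.1**

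| Attribute | Row in overall summary | SOC/PT table |
|---|---|---|
| Any AE | yes | not named |
| TEAE | yes | yes |
| Serious TEAE | yes | yes |
| Related TEAE | yes | yes |
| Serious related TEAE | yes | yes |
| TEAE leading to discontinuation | yes | yes |
| TEAE leading to death | yes | yes |
| Severity grade | none | none |

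That is 7 overall-summary categories and 6 SOC/PT table sets (all TEAEs plus 5 subsets); 0 of the 13 use severity. Causality, introduced alongside severity, has rows and tables of its own (related, serious related). The contrast suggests an omission rather than a decision.

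**2. Where the grade goes.** If no display uses severity, SAP 4.4.1 keeps it out of tables and graphs and puts it in the listings. SAP 4.3.4 has listings accompany the report. So the grade is reported patient by patient, but nothing in the SAP text assures a summary by arm.

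**3. Which events are affected.** A shift in severity between arms stays invisible in the named tables only if all of these hold:
- the events are not classed as serious;
- they do not lead to discontinuation or death;
- the related/unrelated split is the same in the arms compared;
- the numbers of patients per term and overall are the same.

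If any of these fails, at least one named table differs between arms, though without showing severity as the reason.

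**4. Hypothetical example.** Arm size is 20 (60 subjects at 1:1:1, SAP 2.3.1; 60/3 = 20). Every count below is assumed. Let 5 patients per active arm have vomiting, all mild at 50 mg b.i.d., and 4 of the 5 severe at 100 mg b.i.d., under the conditions in step 3.
- Named tables, vomiting: 5/20 = 25% v 5/20 = 25%.
- Severity table, severe vomiting: 0/20 = 0% v 4/20 = 20%.
- Exact (Clopper-Pearson) 95% interval for 4/20: lower limit is the 0.025 quantile of Beta(4, 17) = 5.7%; upper limit is the 0.975 quantile of Beta(5, 16) = 43.7%.
- Fisher's exact test, 0/20 v 4/20, two-sided: 2 × C(20,4)/C(40,4) = 2 × 4,845/91,390 = 0.106. This is for scale only, since the SAP plans no safety tests.

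**5. Would an arm of 20 contain severe events at all?** With an assumed true rate p, the chance of at least one affected patient is 1 − (1 − p)^20:
- p = 5%: 1 − 0.95^20 = 64%
- p = 10%: 1 − 0.90^20 = 88%
- p = 20%: 1 − 0.80^20 = 99%

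At rates in this range, a severity row would probably have something to report.

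**The case against.** The strongest reply is that nothing is lost. Blinded investigators record the grade, it is listed, and with about 60 patients it can be counted by hand. The SAP's Purpose section allows further analyses if they are identified as such, and Protocol Section 4 provides a monitoring board that reviews safety during the trial. All of this stands, and it limits the point to reporting. What the listings lack is a by-arm summary and a rule for a patient with repeated events of different grades. A table added after unblinding would also be post hoc.

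A second reply is that the SAP text may not be the whole plan. The mock TLFs may contain a severity table, and SAP 7.0 can be read as promising a description of every safety parameter, severity included. This also stands in part: the claim can be made only about the SAP text. But SAP 7.0 specifies no severity display, and SAP 8.0 says that the shells may change and may not cover every aspect of the study.

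Third, the affected group is narrower than all severe non-serious events. Protocol 9.4 lets important medical events that may put the patient at risk be classed as serious, so many events graded severe could reach the serious-TEAE tables. The conditions in step 3 of the working reflect this.

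A reader might go further and infer that dose-related severe events would be missing from the safety results. The documents do not support that: the grades are in listings that accompany the report, and the events themselves count in the TEAE and SOC/PT tables.

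A reader might also take the 13-week dog findings ("increased incidence of emesis and salivation (sometimes extreme), and decreased food consumption in 150 mg/kg animals (reversible") as a sign of what to expect in patients. Those are narrative toxicology terms, not Protocol 9.2 grades. Protocol Table 3 puts exposure at the dog NOAEL of 150 mg/kg at 64.3 times (Cmax) and 52.7 times (AUC) the human exposure at 100 mg b.i.d. The protocol's introduction describes that human dose as safe and well tolerated over 28 days. The dog findings carry no weight here.

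**Conclusion.** The point holds as a gap in reporting. SAP 7.1 gives a definite list of displays and none summarises severity by arm, so the first-listed primary objective is left without a by-arm severity summary, and the grade is assured only in listings. The consequence is confined to TEAEs that meet the conditions in step 3 of the working. The 0% v 20% contrast shows how such a difference could be hidden; it is hypothetical and does not forecast any event at these doses. No planned estimate, test or analysis population is affected, and no dose or clinical rule is in question.

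The conclusion assumes that the SAP text is followed as written and that the mock TLFs, which were not available, do not already contain the table. If they do, SAP 7.1 needs only to name it. The change is worth making because it costs almost nothing and supplies a summary that the collected data were designed to support.

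**What to change.** In SAP 7.1:
- add a severe-TEAE row to the overall AE summary (patients with at least one TEAE graded severe, by arm);
- add one table of TEAEs by SOC, preferred term and worst severity per patient (mild, moderate, severe) for placebo, 50 mg b.i.d. and 100 mg b.i.d., on the Safety population;
- state the counting rule: each patient once per preferred term and once per SOC, at the highest grade recorded.

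Keep both descriptive, in line with SAP 7.0, and add matching shells to the mock TLFs. The cost is one row and one standard table, programmed before unblinding from a field already on the AE form. No new data, visits or patients are needed.

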7.2 Vital Signs

The vital signs include blood pressure, temperature, pulse and respiratory rate. For each scheduled visit, summary statistics will be provided (study population size, mean, SD, minimum, median, and maximum) for each vital sign parameter, by treatment level. Summary statistics for change from screening values will also be presented.

7.3 ECG

The 12-lead ECG tests will be summarized using qualitative statistics per each scheduled visit. The summary will include the number and percentage of patients with test values classified as normal, abnormal (clinically significant), abnormal (not clinically significant) and unevaluable.

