5.3. EXCLUSION CRITERIA

Patients meeting any of the following criteria will be excluded from the study:

- 1. Exposure to an experimental drug, experimental biologic or experimental medical device within the longer of 5 half-lives or 3 months before screening
- 2. Enrollment in the previous PTI-125 trial
- 3. A medical condition that would interfere with a lumbar puncture
- 4. Residence in a skilled nursing facility and requiring 24 h care.
- 5. Clinically significant laboratory test results

- 6. Clinically significant untreated hypothyroidism (if treated, thyroid-stimulating hormone level and thyroid supplementation dose must be stable for at least 6 months before screening)
- 7. Insufficiently controlled diabetes mellitus
- 8. Renal insufficiency (serum creatinine > ULN)
- 9. Malignant tumor within 3 years before screening (except squamous and basal cell carcinoma or cervical carcinoma in situ or localized prostate cancer or localized stage 1 bladder cancer)
- 10. History of ischemic colitis or ischemic enterocolitis
- 11. Unstable medical condition that is clinically significant in the judgment of the investigator
- 12. Alanine transaminase (ALT) or aspartate transaminase (AST) > ULN or total bilirubin > ULN.
- 13. History of myocardial infarction or unstable angina within 6 months before screening
- 14. History of more than 1 myocardial infarction within 5 years before screening
- 15. Clinically significant cardiac arrhythmia (including atrial fibrillation), cardiomyopathy, or cardiac conduction defect (patients with a pacemaker are acceptable)
- 16. Symptomatic hypotension, or uncontrolled hypertension
- 17. Clinically significant abnormality on screening electrocardiogram (ECG), including but not necessarily limited to a confirmed QTc value ≥ 450 msec for males or ≥ 470 msec for females.
- 18. Stroke within 18 months before screening, or history of a stroke concomitant with onset of dementia
- History of brain tumor or other clinically significant space-occupying lesion on CT or MRI
- 20. Head trauma with clinically significant loss of consciousness within 12 months before screening or concurrent with the onset of dementia
- 21. Onset of dementia secondary to cardiac arrest, surgery with general anesthesia, or resuscitation
- 22. Specific degenerative CNS disease diagnosis other than AD (eg, Huntington's disease, Creutzfeld-Jacob disease, Down's syndrome, Frontotemporal Dementia, Parkinson's disease)
- 23. Wernicke's encephalopathy

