7.1. LIVER CHEMISTRY STOPPING CRITERIA

Liver chemistry threshold stopping criteria have been designed to assure patient safety and to evaluate liver event etiology during administration of Study Drug. Administration of Study Drug will be discontinued if any of the following liver chemistry stopping criteria occurs:

- ALT or AST $\geq 2.5 \times ULN$.
- ALT or $AST \ge 2 \times ULN$ and total bilirubin $\ge 2 \times ULN$. Note: Serum bilirubin fractionation should be performed if total bilirubin is $\ge 2 \times ULN$.
- ALT or $AST \ge 2 \times ULN$ if associated with appearance or worsening of a rash or hepatitis symptoms (fatigue, nausea, vomiting, right upper quadrant pain or tenderness, fever, rash or eosinophilia).
- ALP or GGT \geq 2.5 x ULN.

In the event of discontinuation due to liver abnormalities, the patient will be appropriately investigated to determine the potential cause.

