7.4 Laboratory Data

The clinical laboratory assessments include Hematology, biochemistry and Urinalysis. Laboratory data will be converted to International System of Units (SI units), using commonly available conversion factors. Summary statistics will be based on the converted values. The data listings will contain both the original as well as the converted values.

Descriptive statistics (study population size, mean, SD, minimum, median, and maximum) for each laboratory test and their change from screening values will be presented by treatment group for each scheduled visit.

Axiom Fusion eClinical Suite™Configured for the PTI-125-02 StudyPage 20 of 22

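### The SAP's safety tables do not count the patients who meet the protocol's liver stopping criteria, and do not compare each ECG with the patient's own pre-dose tracing

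*SAP*

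**What the plan says.** Safety comes first among the primary objectives in SAP 1.1, and SAP 1.2.5 names clinical laboratory tests and ECG results as safety endpoints.

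- **Liver criteria, Protocol 7.1.** "Administration of Study Drug will be discontinued if any of the following liver chemistry stopping criteria occurs". There are four: (i) ALT or AST at 2.5 × ULN or more; (ii) ALT or AST at 2 × ULN or more together with total bilirubin at 2 × ULN or more; (iii) ALT or AST at 2 × ULN or more with rash or hepatitis symptoms; (iv) ALP or GGT at 2.5 × ULN or more.
- **Laboratory tables, SAP 7.4.** "Descriptive statistics (study population size, mean, SD, minimum, median, and maximum) for each laboratory test and their change from screening values". These are given for every arm and visit, in SI units. No count against a multiple of ULN is described.
- **ECG tables, SAP 7.3.** "The 12-lead ECG tests will be summarized using qualitative statistics per each scheduled visit". What the reader gets is "the number and percentage of patients with test values classified as normal, abnormal (clinically significant), abnormal (not clinically significant", with a last category for unevaluable tracings. Vital signs (SAP 7.2), by contrast, get numeric summaries and change from screening.
- **QTc limits, Protocol 5.3.** They appear only in exclusion criterion 17, for the screening ECG: "a confirmed QTc value ≥ 450 msec for males or ≥ 470 msec for females".
- **Other data.** SAP 4.4.1 sends data not analysed under the plan to listings only. SAP 8.0 places the table shells in a separate document, which was not available.

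**The concern.** Each liver criterion is met by a patient, at a test, relative to a laboratory's limit. Criteria (ii) and (iii) also need two facts about the same patient. A summary of one test at one visit in SI units carries none of this. The liver is a reasonable place to look: the 6-month rat study in Protocol 2 found adverse liver changes at the two upper doses, with an AUC margin of 2.5 at the NOAEL (Table 4).

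For ECGs, criterion 17 excludes only clinically significant screening abnormalities, and criterion 15 accepts pacemakers, so some patients may enter with an abnormal tracing. Counts per visit then mix old and new findings. A QTc rise on a tracing called normal, or abnormal but not clinically significant, would appear as a number in no table that the SAP describes.

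At stake is a basic safety statement for a small placebo-controlled trial: how many patients in each arm met the protocol's own stopping criteria. Without a planned table, it would have to be assembled from listings, with the counting rules chosen after the data are seen.

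**Working it through.** **1. Inputs.** 60 patients in three arms, so 20 per arm (Protocol 4). Criteria from Protocol 7.1 and planned statistics from SAP 7.4. ALT, AST and bilirubin above ULN are exclusions (criterion 12), so patients should start at or below 1 × ULN. The documents give no count or rate on this point to reproduce. The one related figure, the Table 4 AUC margin, does reproduce: 21,200 / 8,483 = 2.5. All patient values below are assumed, in multiples of ULN.

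**2. A single crossing is visible.** With 19 patients at 0.6 and one at 3.0, the mean is (19 × 0.6 + 3.0) / 20 = 0.72 and the median 0.6, but the maximum is 3.0. In general, one patient rising from b to 2.5 moves the mean by (2.5 − b) / 20, which is 0.11 for b = 0.3 and 0.075 for b = 1.0. The mean and median barely react; the maximum does, provided the value enters the table. SAP 4.3.3 takes the most extreme result when scheduled and unscheduled tests share a time point, but admits a repeat test only if the corresponding original was normal. Read literally, a repeat at 3.0 after an original at 1.5 is left out.

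**3. The number of patients is not recoverable.** Take two arms of 20, each with 16 patients at 0.5 and one at 3.0. The other three are 0.8, 2.0, 2.3 in arm A and 1.1, 1.4, 2.6 in arm B.
- Sum of the three: 5.1 in both. Sum of squares: 0.64 + 4.00 + 5.29 = 9.93 and 1.21 + 1.96 + 6.76 = 9.93.
- Both arms: n 20; mean (8.0 + 3.0 + 5.1) / 20 = 0.805; SD √[(22.93 − 20 × 0.805²) / 19] = 0.724; minimum 0.5; median 0.5; maximum 3.0.
- Patients at 2.5 or more: 1 in arm A, 2 in arm B.

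If everyone screened at 0.5, the change-from-screening summaries match too. The tables are also per visit, so a high maximum on Days 14 and 28 may be one patient or two.

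**4. The joint criterion is not recoverable.** ALT: 18 patients at 0.5, one at 2.1, one at 2.2; mean (9.0 + 4.3) / 20 = 0.665, SD 0.508. Bilirubin: 18 at 0.5, one at 2.1, one at 2.0; mean (9.0 + 4.1) / 20 = 0.655, SD 0.477. If the same two patients carry both rises, 2 meet criterion (ii). If different patients carry them, 0 do. Every planned statistic is the same. ALT stays below 2.5, so criterion (i) does not give the case away.

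**5. Multiples of ULN.** A maximum in SI units converts to a multiple of ULN only if the limit that applied to that patient is known. The documents do not say whether one clinical laboratory serves all sites. With one laboratory and one limit it is a simple division; otherwise the tables do not allow it.

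**6. ECG.** SAP 4.3.2 defines baseline as the last value on or before the first treatment date, and Protocol 7.2.3 schedules a pre-dose Day 1 ECG. SAP 7.3 makes no use of that pair. If 3 of 20 tracings are abnormal pre-dose and 3 of 20 on Day 28, the number of patients with a new abnormality can be anything from 0 to 3.

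**7. Scale.** The chance of at least one crossing in an arm is 1 − (1 − p)^20. At assumed true rates of 1%, 2%, 5% and 10% it is 18%, 33%, 64% and 88%. If none of 20 cross, the one-sided 95% upper bound is 1 − 0.05^(1/20) = 13.9%; for none of 40 on active drug it is 7.2%. The counts will be small and descriptive, so each patient matters.

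**The case against.** The case against is substantial, and much of it stands.

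- **No contradiction.** Protocol 10.5 promises only descriptive change from screening for vital signs and laboratory results, and the SAP delivers that. This stands: the point asks for a better display.
- **Adverse events.** Protocol 9.1 makes new clinically significant laboratory or physiological abnormalities adverse events, and SAP 7.1 tabulates treatment-emergent events by preferred term and arm, including those leading to discontinuation. This stands in part. It depends on investigator judgement, and Protocol 7.1 does not say that a crossing must be recorded as an adverse event.
- **Listings and disposition.** With about 20 patients per arm, the listings can be read through. That is a way to recover the information, but no table is planned. SAP 5.1 counts discontinuation of the study, not of study drug.
- **Monitoring board.** It reviews patient safety during the trial (Protocol 4), which does not settle what the report tabulates.
- **Rat data.** The trial lasts 28 days. The 4-week rat margin is 249,000 / 8,483 = 29.4, with the liver change judged adaptive, and a second 6-month rat study has been started to refine the NOAEL. The 2.5 margin is a reason to look, not evidence that a signal is expected.

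A reader might also infer three stronger things that the documents do not support:

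- That passing 450/470 msec on treatment is a protocol-defined event which the SAP ignores. Those values are an entry exclusion; the protocol sets no on-treatment QTc limit.
- That the tables hide any liver crossing. Step 2 shows that a single-test crossing appears as the maximum.
- That a QTc rise ending below 450 msec would be recorded as no change. The documents do not say how on-treatment tracings are classified.

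**Conclusion.** The point holds as a gap in the planned display. No table described in the SAP counts patients who meet any Protocol 7.1 criterion. A single extreme value would be seen, but the number of patients could differ (1 against 2 in step 3) and the joint criterion could differ (2 against 0 in step 4) behind identical tables. ECGs have no within-patient comparison and no numeric QTc.

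This rests on the SAP text alone: the separate table shells may already contain some of these displays, though SAP 8.0 says that they may change and may not reflect every aspect of the study. The patient values and rates in the working are illustrations, not predictions. No figure in the documents changes, and the safety analysis is not invalid without the additions. They are worth making because they cost little and answer the safety question more directly than the planned summaries.

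**What to change.** **SAP 7.4.** Add, by arm, the number and percentage of patients meeting each Protocol 7.1 criterion at any on-treatment test, whether scheduled, unscheduled or repeat, computed as multiples of the reporting laboratory's ULN. Include both combined criteria. State whether the ALT/AST and bilirubin values must come from the same draw, and how the symptom criterion is linked to adverse event records. Say that the repeat-test restriction in SAP 4.3.3 does not apply to this table.

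**SAP 7.3.** Add a shift table by arm from the pre-dose Day 1 ECG category to the worst on-treatment category. Where numeric QTc is captured, add QTc and its change from pre-dose Day 1 by visit and arm. Do not carry the 450/470 msec screening limits over as on-treatment events; any on-treatment QTc categories are for the sponsor to pre-specify before unblinding.

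**Reconcile.** Protocol 4 lists an ECG on Day 7, while Protocol 7.2.4, Appendix A and SAP Table 1 show none, so the scheduled ECG visits in SAP 7.3 are unclear.

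**Cost.** SAP wording and a few extra tables. The liver tests and ECG categories are already planned. The symptom criterion needs a short derivation from adverse event data. If numeric QTc is not already recorded after screening, it needs an eCRF field. No extra patient procedures are required.
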